Aim 3: To conduct preliminary analyses exploring whether emerging adults who receive the intervention demonstrate improvement in key symptom domains. Specifically, 40 youth will be randomized to either the integrated treatment or standard care. Primary outcomes will include substance abuse and PTSD. Secondary outcomes will include criminal justice involvement, adaptive functioning, and other mental health symptoms.

The results of the study will have a **significant impact on public health** by informing treatments for co-occurring SUD/PTSD among justice-involved transition age youth, a group at the highest risk for these problems. Demonstrating the efficacy of an integrated treatment approach will provide a valuable clinical tool for community-based therapists to employ in the context of existing evidence-based treatments. Further, should compelling indications of efficacy be found and safety and acceptability be established, these aims will position the research to advance to an appropriately powered randomized controlled trial.

A. SIGNIFICANCE

Prevalence and consequences of substance use problems among emerging adults. Transition age youth (i.e., emerging adults, ages 18-25) represent the age group with the **highest rates of initiation of substance use, increases in substance use, and progression of substance use into substance use disorders** (Chassin, Flora, & King, 2004; Delucchi, Matzger, & Weisner, 2008; SAMHSA, 2009). Substance use plays a significant role in many serious problems during this developmental period, including suicide (SAMHSA, 2010), automobile accidents (Hingson, Heeren, Winter, & Wechsler, 2005), and other lethal events. Emerging adults with SUDs also have increased rates of risky sexual behavior, increasing their chances of contracting HIV and other STDs (King, Nguyen, Kosterman, Bailey, & Hawkins, 2012). Further, SUDs significantly impede successful negotiation of important developmental tasks of this transitional age, leading to increased rates of unemployment and job instability and decreased college attendance (Bray et al., 2000; Mangione et al., 1999). Finally, emerging adults with SUDs represent a greatly underserved population, with a high likelihood of “slipping through the cracks” as they transition from child to adult substance use service providers ([name], Green, & Hoffman, 2009). **Thus, this group has a very high potential to present significant short- and long-term costs for individuals, families, and society.**

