Random Assignment occurs after the BL evaluation. A computerized urn randomization procedure (Stout et al., 1994) will balance patients on gender and submission of a positive sample for any illicit drug (i.e., cocaine, amphetamine, methamphetamine, opiate, benzodiazepine, or marijuana) at baseline, because positive samples at treatment initiation are related to poor outcomes (Preston et al., 1998; Silverman et al., 1998; Stitzer et al., 2007). Prior to randomizing participants, up to 10 pilot participants will complete a pilot study consent form and study procedures described for Group B below, through month 3 follow-up, for the purpose of monitoring staff on study procedures prior to the randomized trial.

Group A (Standard care [SC]; n=20) patients will receive SC at the substance use clinic where they are seeking treatment. This treatment approach typically consists of group therapy sessions, including daily planning, 12-Step treatment, relapse prevention, coping and life skills training, and AIDS education. Groups are led by recovering individuals, nurses, and masters level counselors. Very few individual sessions are provided at these clinics, and then only in cases of emergencies (e.g., suicidality). These clinics rarely conduct breathalyzers or urine testing for illicit drug use. Any such testing will occur as it normally would, and study procedures will not

impact standard care in any way. If the participant is not already enrolled in SC at a substance use clinic, they will be provided with referrals to clinics convenient to their home.

Study urine samples will be collected twice weekly. Patients will receive a \$5 payment (check or gift cards) for each of 20 urine/breath sample submissions during weeks 1-10. In addition, they will be asked to complete the NSSEP-SS and the CES-D to assess PTSD symptoms and depression weekly. If patients cease attending groups, they will still be encouraged to attend these brief meetings for sample monitoring. To maintain consistency with standard care in these clinics, results from toxicology screens will not be discussed with providers.

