Group B (SC + PE/CM Treatment; n=20) patients will receive the same SC groups as Group A. If they are currently enrolled in substance use treatment, they will continue with that treatment. If not, they will be provided with referrals for substance use treatment in the community. In addition, they will participate in an integrated Contingency Management (CM) and Prolonged Exposure (PE) treatment protocol described subsequently. Either the PI ([name]) or [name], will serve as the study therapist for participants randomized to group B. For cases where [name] serves as the therapist, [name] will provide clinical supervision of study cases.

As in Group A, participants will undergo testing twice weekly with a breathalyzer and urine drug screen. In addition, during the first meeting of the week, participants will engage in both CM and PE components of treatment (described below). During the second meeting of the week, participants will engage in CM and a brief check-in on the components of PE that the participant is working on for homework that week but no new PE-related components will be introduced.

Contingency Management Component. Participants in Group B will participate in CM to target abstinence from substance use. In prize CM protocols, participants earn opportunities to draw cards from a prize bowl. The cards differ in prize value, ranging from \$0 to \$100 in value, and participants can earn increasing numbers of draws with consecutive performance. The variable reinforcement amount feature of prize CM distinguishes it from other reinforcement systems such as voucher CM. Participants will be allowed to draw from the prize bowl if their urine drug screen is negative for opiates, methadone, cocaine, amphetamines, methamphetamines, and marijuana (see additional information about marijuana use below) and their breath screen is negative for alcohol.

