Feasibility measures relevant to recruitment and dropout proportions will be examined with 95% confidence intervals used to estimate the proportion of emerging adults who agree to participate out of the number deemed eligible and to compare those who complete versus do not complete the intervention. Feasibility will be evaluated by examining therapist adherence using ratings of taped sessions as well as emerging adults' responses to qualitative interviews. Measures of safety will include repeat trauma exposure, suicidal ideation, and risky substance use behaviors. Patterns of safety indicators will be examined using frequency distributions and descriptive statistics. In addition, rates of these indicators will be compared across Group A and Group B to determine if there is any increased risk posed by the active treatment compared to treatment as usual. These data will be used to make any necessary protocol changes.

Aim 3: To conduct a preliminary analysis of the efficacy of the integrated protocol in improving symptoms among emerging adults.

Groups will be compared with respect to the primary outcome variables (substance use, PTSD symptoms) and secondary variables (delinquent behaviors, depression, adaptive functioning, HIV risk behaviors). An important issue preceding analyses is to identify baseline differences between groups despite random assignment. Differences between groups that may be related to outcome will be used as covariates or fixed factors, as appropriate. We will conduct intent-to-treat analyses, with all randomized patients and apply random regression models, also known as hierarchical linear models (HLM), to determine if patients improve differentially between groups over time (Raudenbush & Bryk, 2002). HLM is specifically designed for repeated measures designs with missing data, allowing for intra-subject serial correlation and unequal variance and covariance structures over time by incorporating available trend data for each individual with information on the group from which the subject is drawn. Maximum likelihood estimation enables analyses to be performed for the full trial without having to drop subjects with incomplete data, and both continuous and dichotomous variables can be analyzed. If data cannot be normalized, group by time effects will

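### The between-arm safety comparison is meant to determine any increased risk, which 20 patients per arm cannot do; it should be reported as preliminary estimates with confidence intervals

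*Combined protocol and SAP*

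**What the plan says.** In the Data Analysis Strategy, Aim 2 names three kinds of indicator: "Measures of safety will include repeat trauma exposure, suicidal ideation, and risky substance use behaviors". They are summarised descriptively: "Patterns of safety indicators will be examined using frequency distributions and descriptive statistics". A further sentence then adds a comparison of rates between Group A and Group B, and gives it a purpose of its own: "to determine if there is any increased risk posed by the active treatment compared to treatment as usual". The stated use of the results is "These data will be used to make any necessary protocol changes".

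That paragraph gives no test, significance level, confidence interval, margin or threshold for the safety comparison, and no caution about a null result. It does specify 95% confidence intervals for recruitment and dropout proportions.

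The arms are small: "40 youth will be randomized to either the integrated treatment or standard care", with 20 patients each. The section on random assignment has "Group A (Standard care [SC]; n=20) patients will receive SC at the substance use clinic" and "Group B (SC + PE/CM Treatment; n=20) patients will receive the same SC groups as Group A".

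The closing paragraph of the Specific Aims says the work will be positioned for a powered trial "should compelling indications of efficacy be found and safety and acceptability be established". The Overview of Design describes the next step differently. There the trigger is evidence of feasibility, and the data on safety, feasibility and symptom reduction are called preliminary.

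**The concern.** The sentence gives the comparison a property that the design lacks. Twenty patients per arm can reveal a very large excess of events, but they cannot determine whether there is any increase. Without an interval or a caveat, similar rates in the two arms could be taken to show that adding exposure therapy and contingency management carries no extra risk.

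This matters because safety is a named aim of the pilot, the population is high-risk, and one of the indicators is suicidal ideation. The safety statement from this study may also be carried into the application for the next trial. The sample size itself is reasonable for a pilot. The fault lies in the inferential purpose given to the comparison and in the lack of any measure of uncertainty.

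**Working it through.** **Inputs.** From the documents: 20 patients per arm, three safety indicators, and no event rates, test or significance level. There is no stated power or sample-size figure to reproduce. Assumed here: control-arm risks of 5% to 30%, a two-sided Fisher exact test at 5%, and complete follow-up.

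**1. Power.** Let a and b be the event counts in Groups A and B. Power is the sum, over all pairs (a, b) with Fisher p ≤ 0.05, of Bin(a; 20, pA) × Bin(b; 20, pB).

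| Control risk | Power if risk doubles | Power if risk triples |
|---|---|---|
| 5% | 1.7% (v 10%) | 7.0% (v 15%) |
| 10% | 7.2% (v 20%) | 24.2% (v 30%) |
| 15% | 12.4% (v 30%) | 44.3% (v 45%) |
| 20% | 19.2% (v 40%) | 65.0% (v 60%) |
| 25% | 26.9% (v 50%) | 83.4% (v 75%) |
| 30% | 34.7% (v 60%) | 97.9% (v 90%) |

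A doubling is more likely missed than found at every control rate in the range. A tripling is more likely missed up to a control rate of 15%, and more likely found from 20%.

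**2. Sensitivity to the method.** A one-sided Fisher test raises 10% v 20% only to 10.9%, and 20% v 40% to 29.0%. The two-sided normal approximation gives 13.9% and 27.6%. With 18 per arm (10% loss), two-sided Fisher power falls to 6.0% and 15.9%.

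**3. Smallest increase detectable with 80% power (two-sided Fisher, 20 per arm).**
- Control 5%: Group B risk 45%, an increase of 40 points.
- Control 10%: 53%, an increase of 43 points.
- Control 20%: 68%, an increase of 48 points.
- Control 30%: 78%, an increase of 48 points.

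**4. Counts needed for significance.** With 0/20 in Group A, 4/20 in Group B gives p = 0.106 and 5/20 gives p = 0.047. Five events against none is the smallest significant split.

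**5. What reassuring data would leave open.** These results need no assumed rate and no test.
- No events in 20: the Clopper-Pearson two-sided upper limit is 1 − 0.025^(1/20) = 16.8%.
- An event with a true risk of 5% is not seen at all in 20 patients with probability 0.95^20 = 0.358, or 36%.
- 3/20 in each arm: the Wilson limits for 15% are 5.24% and 36.04%. The Newcombe half-width is √[(0.150 − 0.0524)² + (0.3604 − 0.150)²] = √(0.0095 + 0.0443) = 0.232. The interval for the difference is about −23 to +23 points.
- 0/20 in each arm: the same method gives about −16 to +16 points.

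**The case against.** The strongest reply has five parts.

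- **No test is planned.** The section says rates will be compared and names no significance rule, so power is the reviewer's construct, as are all the event rates. This is correct, and the power figures are conditional on those assumptions. The interval widths in step 5 need neither, and they lead to the same conclusion.
- **Large relative increases could be found.** A reader might infer that the trial would miss any doubling or tripling. That is too general: power for a tripling is 65% from a 20% control rate and 83% from 25%. One indicator is risky substance use, in patients who must all have a substance use disorder, so a high base rate cannot be excluded.
- **Nobody says a null means safe.** A reader might infer that the investigators will treat a null comparison as proof of safety. No passage says so, and the one stated use is to inform protocol changes. The documents support only that it could be misread so, because nothing in the Aim 2 text prevents it.
- **The condition is loose.** The Specific Aims do not tie established safety to the comparison between the arms, and the Overview of Design calls the safety data preliminary. This weakens any claim of a formal safety gate. It also shows that the two passages need the same wording.
- **Participants are protected in other ways.** Checks at each session, weekly symptom measures, adverse event review and IRB reporting do not depend on this comparison. That stands, but case-level monitoring does not answer the between-arm question that the sentence poses.

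**Conclusion.** The concern holds as a fault in the stated purpose and reporting of the safety comparison. Under assumed control rates of 5% to 30%, power to detect a doubling is about 2% to 35%, and 80% power needs an increase of 40 points or more by the two-sided Fisher test. Without those assumptions, no events in 20 is still compatible with a risk of up to 16.8%, and equal counts of three leave an excess of up to about 23 points open. The comparison therefore cannot determine whether there is any increased risk.

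The documents do not support reading this as a failure to protect participants, as a need for a larger pilot, or as a declared plan to equate no difference with safety. The correction is worth making, because it changes what the pilot can fairly conclude about one of its named aims.

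**What to change.** In the Data Analysis Strategy, Aim 2, replace the clause that states the purpose of the between-arm comparison with:

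> For each safety indicator, the rate in each group and the risk difference (Group B minus Group A) will be reported with a 95% score or exact confidence interval. The comparison is preliminary: absence of a difference will not be read as absence of increased risk, and the upper confidence limit will be reported as the largest excess risk compatible with the data.

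In the closing paragraph of the Specific Aims, replace the reference to established safety with wording that agrees with the Overview of Design, for example that preliminary safety data show no signal of concern. No numerical limit belongs there, since it will be a result of the trial.

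The cost is a few lines of analysis and a less favourable safety statement. Sample size, recruitment and study procedures do not change.

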Subjects and settings: Subjects will be 40 patients seeking substance abuse treatment. In addition, up to 10 pilot participants will be recruited to test study procedures. Pilot participants will not be randomized and all will receive the experimental treatment – see below for additional details. A subset of patients will be recruited from the Farrell Center (New Britain, CT) and at The Village for Families & Children (Hartford, CT). These participants will receive study treatment at their respective treatment centers. Additional participants will be recruited through flyers at other substance abuse treatment centers in the area and through ads. These participants will receive the study treatment at UConn Health in Farmington.

To aid with study recruitment, participants who are randomized into the study will be given flyers to hand out to peers who are in their age group and who may use drugs or alcohol. Participation in the study will not be affected by whether or not a subject chooses to send referrals. The flyer will describe the study and include RA contact information. A unique code will be used to link returned flyers with the original participant. Subjects can earn \$15 for each eligible recruit (up to 3 referrals) who attends an intake appointment regardless of whether the recruit consents to participate in the study.

Participant inclusion/exclusion criteria. Participants must meet the following inclusion criteria: (a) 18-25 years old; (b) meets diagnostic criteria for substance use disorder; (c) meets diagnostic criteria for full or subthreshold PTSD; (d) currently able to provide a urine drug screen that is negative for cocaine and non-prescribed methadone or opiates in the past 60 days (since we are not able to test for methadone or determine whether a positive test for opiates is from a prescribed or non-prescribed source, we will rely on patient self-reports to make final decisions about the methadone and opiate results); and (e) speaks English.

Exclusion criteria are: (a) significant cognitive impairment or serious uncontrolled psychiatric problem (other than PTSD); (b) in recovery from pathological gambling or current pathological gambling diagnosis and desiring

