It is expected that, for some emerging adults, marijuana will be their drug of choice. Marijuana treatment requires a different CM schedule, as marijuana can continue to be detected on urine drug screens for up to 3-4 weeks following last use among heavy marijuana users. In these cases, participants will earn 1 draw simply for attending sessions and providing a urine sample for the first 4 weeks of CM treatment. Once the participant is able to provide a negative screen, they will begin to earn escalating rewards starting at the same level as their peers who are in treatment for other illicit drugs. For example, if a participant is positive for marijuana until week 3, s/he would receive one draw for each session attended leading up to the negative screen and then 5 draws for his/her negative urine drug screen in week 3. Once the participant tests negative for marijuana (or the 4 weeks has elapsed), s/he is subject to the same rules for negative and positive screens as other participants.

This adaptation allows us to engage marijuana users in the CM treatment process during the time that they are waiting for their urine drug screens to reflect their abstinence.

Prolonged Exposure Therapy. Participants in Group B will also engage in Prolonged Exposure (PE) therapy for the treatment of PTSD. PE is a well-established treatment for PTSD for a wide range of populations, including victims of sexual and/or physical assault, childhood trauma, accidents, and war veterans. A 2010 meta-analysis reviewed 13 randomized controlled trials evaluating PE over 20 years and concluded that this treatment approach "is a highly effective treatment for PTSD, resulting in substantial treatment gains that are maintained over time" (Powers, Halpern, Ferenschak, Gillihan, & Foa, 2010). PE has also been evaluated with patients who have co-occurring PTSD and substance abuse disorders, resulting in evidence for its safety, feasibility, and efficacy with this patient population (Brady, Dansky, Back, Foa, & Carroll, 2001; Foa et al., 2013; Mills et al., 2012).

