be assessed with HLM, coding patients as improved or not at each time point. The main analyses will focus on during treatment effects (baseline through follow-up) but long-term effects (baseline to 3-month post-treatment follow-up) will also be analyzed (see follow-up section).

The primary outcomes are substance use is longest duration of abstinence from illicit drug use and symptoms of PTSD (NSESP-SS), continuous variables that can be transformed if needed. The primary substance use outcome is longest duration of abstinence from substances (LDA), the main outcome variable in most CM trials and the variable most strongly associated with long-term abstinence (Higgins et al., 1994, 2000, 2003; Petry et al., 2005). Linear regression will evaluate group differences in LDA, with condition as the independent variable (along with any important covariates). If data cannot be normalized, nonparametric tests will be used. While LDA is the primary substance use outcome measure, it is affected by retention as missing samples break a string of abstinence (unless preceded and followed by negative samples, and an excused 'miss' is obtained due to documented illness, court appearances, etc. usually comprising <5% of missed samples). Proportion of negative samples, in contrast, is unaffected by missing samples. Thus, we will also analyze proportion of samples negative for substances as a secondary outcome using similar analyses.

Analyses will focus on the 10-week during treatment effects, but long-term effects will also be analyzed. These will involve logistic regressions to predict substance abstinence at the 3-month follow-up, with treatment group and any important baseline characteristics (e.g., baseline sample result) included as independent variables. HLM analyses for dichotomous measures will also be conducted to evaluate substance abstinence over time between treatments from baseline throughout the 3-month follow-up. Additional secondary drug use outcomes will investigate abstinence from all substances concurrently and from each of the other drugs independently. These analyses will parallel those outlined above.

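### The regression for longest duration of abstinence (LDA) should include the urn factors as fixed terms; the plan picks covariates by observed imbalance, which the urn suppresses

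*Combined protocol and SAP*

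**What the plan says.** The Random Assignment section uses an urn that "will balance patients on gender and submission of a positive sample for any illicit drug". The reason given for the second factor is "because positive samples at treatment initiation are related to poor outcomes". No reason is given for gender.

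Data Analysis Strategy, Aim 3, opens its treatment of covariates with "An important issue preceding analyses is to identify baseline differences between groups despite random assignment", and continues: "Differences between groups that may be related to outcome will be used as covariates or fixed factors, as appropriate". It names no test, cut-off or candidate variables.

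LDA is the primary substance use outcome. It is analysed by linear regression "with condition as the independent variable (along with any important covariates"). No covariate is named, and the nonparametric fallback names none either. Proportion of negative samples, a secondary outcome, is to be analysed in a similar way.

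The analysis plan mentions the baseline sample result once, as an example, for the logistic regression of abstinence at the 3-month follow-up: "with treatment group and any important baseline characteristics (e.g., baseline sample result) included as independent variables".

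**The concern.** A rule that admits a covariate because the arms differ on it works worst for a factor the design has balanced. The urn makes a visible difference in the baseline sample unlikely, so the rule tends to leave out the one variable that the protocol itself calls prognostic. Balancing in the design without adjusting in the analysis leaves the factor's variance in the residual, although the urn has already removed most of its effect on the estimate. The reported standard error is then too large.

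Because the trigger is unstated, the model for a primary outcome also depends on a judgement made after the baseline data are seen. At stake are the width of the LDA interval and some power, in a pilot whose results are meant to support an application for a fully powered trial. The NSESP-SS group-by-time model and the other Aim 3 models are not in question.

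**Working it through.** The plan gives no alpha, effect size, SD or power for LDA, so there is no figure of its own to reproduce.

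**Inputs from the documents.** 20 per arm (Group A and Group B descriptions); 40% women (Inclusion of Women and Minorities); twice-weekly samples for 10 weeks, so 20 samples; marijuana detectable for up to 3-4 weeks in heavy users (Contingency Management Component).

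**Assumptions.** Two-sided 5% test; 50% baseline-positive (30% and 70% gave the same pattern); an urn starting with one ball per arm and adding one opposite-arm ball per assignment, drawn from the more imbalanced factor; R², the share of within-arm outcome variance explained by the baseline sample, from 0 to 0.3.

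**Step 1: how often the rule would select the baseline sample.** It differs between arms at p<0.05 in 0.2% of simulated trials, at p<0.20 in 6%, and by 10 percentage points or more in 41%. Varying the urn settings and prevalence gives 0.03-0.4% at p<0.05, against about 4-6% without balancing. The answer therefore depends on the trigger, which the plan does not state.

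**Step 2: hand check of the standard error.** Set the within-arm SD to 1 and the positive share to p = 0.5. The effect of the baseline sample is b = √(R²/[p(1−p)]), so at R² = 0.2, b² = 0.2/0.25 = 0.8. The between-arm difference in positive share has an SD of about 0.107 under this urn.

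- Reported unadjusted SE: √(2/20) = 0.316.
- True unadjusted SD: √[(1−R²)(2/20) + b² × 0.107²] = √(0.080 + 0.8 × 0.01145) = √0.0892 = 0.299.
- Ratio: 0.316/0.299 = 1.06.

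Without balancing, the SD of the difference is about 0.157. The same formula then gives √(0.080 + 0.8 × 0.0246) = 0.316, equal to the reported SE. The mismatch comes from balancing without adjusting.

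**Step 3: simulation, normal outcome** (40,000 trials per cell; unadjusted / adjusted for both urn factors).

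| R² | True SD | Reported SE | Type I error, % | Power at 0.5 SD, % | Power at 0.8 SD, % |
|---|---|---|---|---|---|
| 0 | 0.318 / 0.322 | 0.315 / 0.319 | 5.1 / 5.1 | 33 / 32 | 68 / 67 |
| 0.1 | 0.308 / 0.304 | 0.315 / 0.303 | 4.4 / 4.9 | 33 / 36 | 70 / 72 |
| 0.2 | 0.300 / 0.288 | 0.316 / 0.286 | 3.8 / 5.0 | 32 / 40 | 70 / 77 |
| 0.3 | 0.292 / 0.270 | 0.316 / 0.267 | 3.2 / 5.0 | 32 / 44 | 70 / 82 |

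The true gain in precision is small: (0.308−0.304)/0.308 = 1% at R² = 0.1 and (0.300−0.288)/0.300 = 4% at 0.2. The rest of the power gain comes from correcting an inflated reported SE. At R² = 0.05 the true SD is 0.313 either way, and power at 0.5 SD is 33% against 34%.

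**Step 4: LDA-shaped outcome** (bounded 0-10 weeks, skewed, runs broken by missed samples; two assumed processes; effects 0.5-0.8 SD).

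| R² | Change in regression power, points | Stratified vs unstratified rank test, points |
|---|---|---|
| 0 | −1 | −1 to −2 |
| 0.1 | +1 to +2 | +1 to +4 |
| 0.2 | +4 to +7 | +5 to +13 |

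At R² = 0.2 the unadjusted SE is 3-4% too large and the adjusted SE 2-3% too small. Type I error is 3.2-3.5% unadjusted and 4.3-4.9% adjusted.

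**Step 5: marijuana carry-over alone**, with no difference in behaviour. For LDA, R² is 0.01 if half of the baseline positives are affected and 0.03-0.05 if all are; power at 0.5 SD changes by −1 to +1 point. For proportion negative, R² is 0.04-0.07 and 0.18-0.28, with gains of +1 to +3 and +9 to +17 points.

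**The case against.** The strongest objection is that the factor may predict little in this trial. Criterion (d) requires participants to be "currently able to provide a urine drug screen that is negative for cocaine and non-prescribed methadone or opiates in the past 60 days", while the titles of the studies cited for the prognostic claim concern cocaine or stimulants. The positives that remain are mainly marijuana, amphetamines and benzodiazepines. For marijuana the protocol says that "marijuana can continue to be detected on urine drug screens for up to 3-4 weeks following last use among heavy marijuana users", but Step 5 shows that this alone barely matters for LDA. The large gains there belong to a secondary outcome and assume that every positive is affected. The plan also describes LDA both as abstinence from illicit drugs and as abstinence from substances; if alcohol counts, a factor that ignores alcohol could predict LDA less well. All of this stands, and it limits the likely size.

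A second objection is that the plan already points towards inclusion. The LDA sentence does not require an imbalance, and the 3-month model names the baseline result as an example of an important characteristic. A reader may infer that it belongs in the LDA model too, but nothing commits to it.

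Third, the plan states no significance trigger, and a 10-point gap judged by eye would occur in 41% of trials. That is correct. It means that selection would turn on which unstated trigger is applied.

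Fourth, Aim 3 is exploratory, the documents give no prognostic reason for gender, and for an LDA-shaped outcome the adjusted SE errs slightly in the other direction. These points lower the weight but do not favour choosing covariates by imbalance.

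**Conclusion.** The concern holds. The LDA regression is not committed to either urn factor, and the general covariate rule is poorly suited to a factor that the urn balances. If the baseline sample explains 10-20% of LDA variance, the unadjusted SE is about 2-5% too large under a normal outcome. Power at 0.5-0.8 SD is then about 1 to 8 points lower than with adjustment, across the normal and LDA-shaped regressions. If it explains 5% or less, the difference is about 1 point either way.

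Nothing here biases the estimate or inflates false positives; the unadjusted test is mildly conservative. R², effect size, outcome shape, the share baseline-positive and the urn parameters are all assumptions. This is a worthwhile, cheap improvement to an exploratory analysis, not an error of validity.

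**What to change.** In the LDA regression and the parallel proportion-negative analysis, pre-specify condition, baseline sample result (positive for any illicit drug, defined as for the urn) and gender as fixed terms, whatever the observed balance. State that covariates for these two models will not be chosen by observed imbalance.

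If LDA cannot be normalized, use a van Elteren test stratified on the baseline sample result. Leave gender out of the strata: with 16 women, 24 men and half positive, the four cells would hold about 8, 8, 12 and 12 people. Show the unadjusted LDA result as a sensitivity analysis.

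The change is wording only, since both variables are recorded at randomization. It uses two degrees of freedom (residual 40 − 4 = 36 instead of 40 − 2 = 38). If the baseline sample is not prognostic it costs about 1 power point, or 1 to 2 for the stratified rank test.
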